2.5 Phase I dose Escalation of Doxorubicin

A dose limiting toxicity (DLT) will be defined as a possibly-related, unexpected SAE of grade 3 or higher or any adverse event at least possibly related to either agent requiring discontinuation of either drug. The DLT monitoring period will be six weeks (2 cycles) after the patient receives both Doxorubicin and Pembrolizumab.

The Phase I dose escalation will use a “3+3” phase I trial design. All patients will receive a flat dose of 200 mg Pembrolizumab every 3 weeks. Patients will have “priming” with a dose of single agent Pembrolizumab before receiving the combination of Pembrolizumab with doxorubicin. Three patients will be treated at the 45mg/m² dose of doxorubicin. Although this is lower and has considerably less toxicity than the standard of care dosing of 75 mg/m², this dose has clinical activity and is still within the range of acceptable dosing, particularly for sarcoma patients with poor performance status or comorbidities (O'Bryan, Baker et al. 1977). In order to prevent accumulation of unexpected serious adverse events (SAEs), the second patient will not start treatment with Pembrolizumab until 10 days after the first patient has received the combination of Pembrolizumab with doxorubicin. Patients will be monitored for adverse events that might be study related until their last study related visit 30 days after discontinuation of therapy. If the first patient develops a DLT, a data safety monitor board (DSMB) will meet before the second patient is treated in order to discuss the toxicity and make recommendations regarding trial modifications.

If at least one of the first three patients develops DLT, a total of six patients will be treated at this dose level. If two patients develop DLT at the 45mg/m² dose level, the trial will immediately stop accrual and a data safety monitoring board (DSMB) will meet to discuss whether to modify, stop or continue the trial.

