Dose escalation to the 75 mg/m² dose of doxorubicin will be contingent upon acceptable safety data following the combination of Pembrolizumab and doxorubicin at the 45 mg/m² dosing. If only one of the six patients develops a DLT, a DSMB will meet prior to dose escalation to review the specific nature of the toxicity and determine if any protocol modifications are necessary prior to proceeding with the dose escalation. If there is no DLT among the first three patients, the trial may proceed immediately to the 75 mg/m² once the third patient receives cycle three (the second cycle including both Pembrolizumab and doxorubicin) without DSMB review.

As was done in the previous cohort, the second patient at the 75 mg/m² dose will not start treatment until 10 days after the first patient has received the combination of Pembrolizumab and doxorubicin at the 75 mg/m² dose level. If the first patient treated has a DLT, a DSMB will meet prior to treatment of the second patient. If two of the first six patients treated using 75 mg/m² doxorubicin develop a DLT, the phase II extension will occur using the 45 mg/m² dosing. The DSMB will meet prior to the phase II expansion. After this, the DSMB will continue to meet at least every six months while the study is enrolling.

[figure not shown]
During the dose escalation period of the trial (up to the first six patients at each dose level), patients will be monitored for 4 hours in the clinical trials unit after receiving their first infusion with the drug combination; monitoring is not required for the Cycle 1 dose of single agent pembrolizumab. After this first combination dose, patients may leave the infusion center immediately after receiving their infusions.

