5.2.2 Timing of Dose Administration

Trial treatment should be administered on Day 1 of each 21-day cycle after all procedures/assessments have been completed as detailed on the Trial Flow Chart (Section 6.0). Trial treatment may be administered up to 3 days before or after the scheduled Day 1 of each cycle due to administrative reasons.

All trial treatments will be administered on an outpatient basis.

Pembrolizumab will be administered as a 30 minute IV infusion every 3 weeks. Sites should make every effort to target infusion timing to be as close to 30 minutes as possible.

However, given the variability of infusion pumps from site to site, a window of -5 minutes and +10 minutes is permitted (i.e., infusion time is 30 minutes: -5 min/+10 min).

The Pharmacy Manual contains specific instructions for the preparation of the pembrolizumab infusion fluid and administration of infusion solution.

Doxorubicin is typically given over a 1-hour infusion but this could be stretched to 3 hours for relief of acute symptoms such as nausea.

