8.2 Statistical Analysis Plan

Phase I Design:

The primary objective of the phase I component of this study is to evaluate the safety of Pembrolizumab given in combination with Doxorubicin among patients with advanced soft tissue sarcoma. The phase I component of this study will use a 3+3 design to evaluate the 45 mg/m² and 75 mg/m² Doxorubicin dosing in combination with Pembrolizumab. Dose-limited toxicities will be evaluated through the end of the first cycle combining Pembrolizumab with Doxorubicin.

The study design is as follows:

- Initially enroll 3 patients into the 45 mg/m² cohort
 - If 2 of 3 experience a DLT, stop and conclude that Pembrolizumab may not be given safely with Doxorubicin at the protocol-specified dose levels.
 - If 1 of 3 patients experiences a DLT, enroll 3 more patients.
 - If less than 2 of 6 experiences a DLT then initiate enrollment to the 75 mg/m² cohort.
 - If 2 or more experience a DLT, stop and conclude that Pembrolizumab may not be given safely with Doxorubicin at the protocol-specified dose levels. Should this occur, discussions will initiate with the DSMB and Merck about whether the protocol could be altered to make the regimen safe or whether the study should be halted.
 - If 0 of 3 patients experience a DLT then initiate enrollment to the 75 mg/m² cohort
- If 45 mg/m² is determined safe, enroll 3 patients into the 75 mg/m² cohort
 - If 2 of 3 experience a DLT stop and conclude that the MTD is 45 mg/m²
 - If less than 2 of 3 patients experience a DLT, enroll 3 more patients.
 - If less than 2 of 6 experience a DLT then conclude 75 mg/m² is the MTD
 - If 2 or more experience a DLT, stop and conclude that that the MTD is 45 mg/m²

The maximum sample size for the phase I component is 12 patients.

Phase II Design:

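### Sections 2.5 and 8.2 set different DLT windows (six weeks and three weeks), so a DLT in weeks 4 to 6 can reverse the 75 mg/m² decision

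*Combined protocol and SAP*

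**What the plan says.** Section 2.5 sets the window: "The DLT monitoring period will be six weeks (2 cycles) after the patient receives both Doxorubicin and Pembrolizumab". Section 8.2, under the phase I design, sets another: "Dose-limited toxicities will be evaluated through the end of the first cycle combining Pembrolizumab with Doxorubicin". Cycles last 21 days (section 5.2.2), so these are 42 and 21 days from the same starting point.

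Decisions that depend on the count:

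- At 45 mg/m², section 2.5: "If at least one of the first three patients develops DLT, a total of six patients will be treated at this dose level". Two DLTs stop accrual pending the DSMB.
- At 45 mg/m² with no DLT among the first three, section 2.5: "the trial may proceed immediately to the 75 mg/m² once the third patient receives cycle three". Cycle 3 is the second combination cycle, and no DSMB review is needed first.
- At 75 mg/m², section 2.5: "If two of the first six patients treated using 75 mg/m² doxorubicin develop a DLT, the phase II extension will occur" at 45 mg/m². Section 8.2 declares 75 mg/m² the MTD if fewer than two of six have a DLT, and 45 mg/m² otherwise.

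Three provisions affect timing. Every patient starts "with a dose of single agent Pembrolizumab before receiving the combination of Pembrolizumab with doxorubicin". At the higher dose, "the second patient at the 75 mg/m² dose will not start treatment until 10 days after the first patient has received the combination". Section 5.2.2 adds: "Trial treatment may be administered up to 3 days before or after the scheduled Day 1 of each cycle due to administrative reasons".

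**The concern.** A 3+3 design turns a small count into a dose, so the period over which events are counted is part of the decision rule. Here the rule has two versions, and nothing in the available text says which governs. An event in weeks 4 to 6 is a DLT for section 2.5 and not for section 8.2. The result at 75 mg/m² bears on the dose for up to 35 phase II patients.

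The cycle 3 trigger has the same root. It falls when section 8.2's window closes but halfway through section 2.5's. If a 45 mg/m² patient then has a DLT in weeks 4 to 6, section 2.5 requires six patients at that dose. The available text does not say what happens to a 75 mg/m² patient who has already been primed or dosed.

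**Working it through.** **The plan's own figure.** Two cycles × 21 days = 42 days = six weeks, so section 2.5's window is internally consistent. Section 8.2's window is 1 × 21 = 21 days.

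**A case needing no assumed rate.** Take six patients at 75 mg/m², one with a DLT in week 2 and another with one in week 5.

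- Section 2.5 counts 2 of 6, so phase II uses 45 mg/m².
- Section 8.2 counts 1 of 6, so 75 mg/m² is the MTD.

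**How often the counts disagree.** The documents give no DLT rates or timing. I assume a six-week rate *p* of 10%, 20% or 33%, with either half of DLTs in weeks 4–6 (uniform timing, three-week rate 0.5*p*) or a quarter (0.75*p*). Events counted under section 8.2 are a subset of those under section 2.5, so the chance of opposite results is the difference of two probabilities.

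At 75 mg/m², P(2 or more of 6) = 1 − (1−*p*)^6 − 6*p*(1−*p*)^5:

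| Six-week rate | Section 2.5 | Section 8.2, uniform | Opposite | Section 8.2, quarter late | Opposite |
|---|---|---|---|---|---|
| 10% | 0.1143 | 0.0328 | 8.1% | 0.0689 | 4.5% |
| 20% | 0.3446 | 0.1143 | 23.0% | 0.2235 | 12.1% |
| 33% | 0.6422 | 0.2592 | 38.3% | 0.4601 | 18.2% |

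At 45 mg/m², P(gate passed) = (1−*p*)^3 + 3*p*(1−*p*)^5. With uniform timing the values under sections 2.5 and 8.2 are 0.9061 and 0.9734, 0.7086 and 0.9061, and 0.4344 and 0.7831. The differences are 6.7, 19.8 and 34.9 points. A pass with 1 of 6 still needs DSMB review under section 2.5.

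**Early exposure at the step to 75 mg/m².** Let day 0 be the third 45 mg/m² patient's first combination dose, so that patient's window closes on day 42. Suppose a 75 mg/m² patient starts priming on the day of the trigger.

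- Nominal: 21 + 21 = day 42, which is 0 days early.
- The 75 mg/m² patient's cycle 2 given 3 days early: 21 + 18 = day 39, 3 days early.
- Patient 3's cycle 3 also 3 days early: 18 + 18 = day 36, 6 days early.
- Patient 3's cycle 2 also 3 days late on a fixed calendar: 15 + 18 = day 33, 9 days early.

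With *p* = 33%, uniform timing and only patient 3's window open, the chance of reading 0 of 3 is (1−*p*)²(1−*pd*/42), where *d* is the days observed. It moves from 0.3008 at *d* = 42 to 0.3113, 0.3219 and 0.3325 at *d* = 39, 36 and 33. That is a rise of about 1, 2 and 3 points.

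Section 2.5 sets no lag between patients 2 and 3. If patient 2's first combination dose came 7 to 21 days after patient 3's (an assumption), the first 75 mg/m² dose would nominally fall on day 35 to day 21 of patient 2's window.

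**The case against.** The strongest reply is that the documents lean on section 2.5 and place a DSMB in the way. Section 5.2 refers back to section 2.5 for the DLT definition, and only section 2.5 assigns the phase II dose from the count. The DSMB meets before the phase II expansion and, under Appendix A, reviews all grade 3 or greater toxicities and SAEs. A serious week-5 event would therefore be seen. In phase II, a DLT-type event triggers a DSMB meeting, and two halt enrollment (section 2.6). All of this stands, and it is why the percentages above must not be read as the chance of treating phase II at the wrong dose. It does not remove the conflict. Section 5.2 repeats the definition but not the window, section 8.2 is the statistical plan, and the DSMB would have two counts before it.

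A reader might infer that 75 mg/m² doxorubicin is routinely given three weeks too early. The documents do not support that: the pembrolizumab-only cycle nominally moves the dose to the close of patient 3's window. The 10-day stagger limits early exposure to about one patient, and section 2.1 describes 75 mg/m² as the standard dose.

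It can also be said that three weeks was intended, since the trigger agrees with section 8.2 and section 2.3 bars growth factor only in cycle 2. That is possible, but then section 2.5 needs changing. Lastly, figures in sections 2.5 and 2.7 are not visible here, so the absence of a hold is established for the text only.

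**Conclusion.** The inconsistency is real and rests on the wording alone: six weeks in section 2.5, three in section 8.2, with opposite results possible from the same patients. Its size depends on assumed rates. The two counts conflict at 75 mg/m² in about 8%, 23% and 38% of trials for six-week rates of 10%, 20% and 33% with uniform timing, or about 5%, 12% and 18% if a quarter of DLTs are late. The 33% rate is a high illustration, because the SAE limb of the DLT definition counts only unexpected events.

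The cycle 3 trigger is a lesser matter. Early exposure is nominally nil and reaches 6 to 9 days only when visit windows stack in one direction. It could be longer only if patient 2's window closes after patient 3's. The plan should be corrected, but nothing here shows that the dose escalation is unsafe.

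**What to change.** 1. State one DLT window in both sections: six weeks (two cycles) from the first combination dose, as section 2.5 already specifies.
2. Keep the cycle 3 trigger for pembrolizumab priming only, and add to section 2.5: *No patient receives 75 mg/m² doxorubicin until all 45 mg/m² patients have completed the six-week DLT period. If one DLT appears during this hold, the 45 mg/m² cohort expands to six and the primed patient joins it; if two appear, accrual stops and the DSMB decides the primed patient's treatment.*

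The cost is wording, with no new procedure, and the phase I maximum stays at 6 + 6 = 12. The hold adds nominally 0 days, and about 6 to 9 days at the visit-window extremes if patient 3's window is the last to close. If patient 2's closes later, the hold lasts longer by that lag. Section 2.3 allows pembrolizumab to be given while doxorubicin is delayed.

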2.6 Phase II extension

[figure not shown]
The phase II extension will use a SWOG 2-stage design (modified Simon's 2 stage design) in order to detect a response rate (CR + PR) of 35%. This is based on a predicted overall response rate for single agent doxorubicin of 15%. 20 patients will be treated in the first stage. If 2 or more patients have CR or PR, an additional 15 patients will be treated. If at least 10 CR or PR's are seen, this will be considered a positive study. Patients treated in the phase I portion of the study will not be included in the phase II analysis. Any toxicity defined as a DLT for the phase I portion will also trigger a meeting of the DSMB during the phase II portion of the trial. Should 2 of these events occur, enrollment must halt until the DSMB meets.

2.7 Trial Diagram

A: Treatment Schedule Diagram

B: Study Design Diagram

3.0 OBJECTIVES & HYPOTHESES

3.1 Primary Objectives & Hypotheses

3.1.1 Objective: To assess the safety and tolerability of the combination of Pembrolizumab and Doxorubicin in patients with advanced soft tissue sarcoma (STS).

Hypothesis: The combination of Doxorubicin and Pembrolizumab will be similar to the toxicity of standard Doxorubicin and Pembrolizumab therapy when these drugs are used as single agents.

3.1.2 Objective: To assess the clinical response rate of advanced soft tissue sarcoma (STS) patients receiving the combination of Pembrolizumab and Doxorubicin.

Hypothesis: The addition of Pembrolizumab to Doxorubicin will result in a 20% increase in the objective response rate (CR + PR) compared with historical controls.

3.2 Secondary Objectives & Hypotheses

Objective: To explore the clinical activity of Pembrolizumab in subjects with advanced STS with respect to the following endpoints:

- Time to response
- Duration of response
- Progression-free survival (PFS)
- Overall survival

Hypothesis: Induction of a meaningful objective response rate with Pembrolizumab will be reflected in other clinical outcome parameters including duration of response, progression-free survival, and overall survival.

3.3 Exploratory Objective

Objective: To compare response rates between patients with high levels of PD-L1 expression with those who have PD-L1 absent.

Hypothesis: Patients with very strong PD-L1 expression will have more profound responses than those with weak or absent PD-L1 expression.

4.0 BACKGROUND & RATIONALE

4.1 Background

Refer to the Investigator's Brochure (IB)/approved labeling for detailed background information on Pembrolizumab.

4.1.1 Pharmaceutical and Therapeutic Background

The importance of intact immune surveillance in controlling outgrowth of neoplastic transformation has been known for decades. Accumulating evidence shows a correlation between tumor-infiltrating lymphocytes (TILs) in cancer tissue and favorable prognosis in various malignancies. In particular, the presence of CD8+ T-cells and the ratio of CD8+ effector T-cells / FoxP3+ regulatory T-cells seems to correlate with improved prognosis and long-term survival in many solid tumors.

The PD-1 receptor-ligand interaction is a major pathway hijacked by tumors to suppress immune control. The normal function of PD-1, expressed on the cell surface of activated T-cells under healthy conditions, is to down-modulate unwanted or excessive immune responses, including autoimmune reactions. PD-1 (encoded by the gene *Pdcd1*) is an Ig superfamily member related to CD28 and CTLA-4 that has been shown to negatively regulate antigen receptor signaling upon engagement of its ligands (PD-L1 and/or PD-L2). The structure of murine PD-1 has been resolved. PD-1 and family members are type I transmembrane glycoproteins containing an Ig Variable-type (V-type) domain responsible for ligand binding and a cytoplasmic tail which is responsible for the binding of signaling molecules. The cytoplasmic tail of PD-1 contains 2 tyrosine-based signaling motifs, an immunoreceptor tyrosine-based inhibition motif (ITIM) and an immunoreceptor tyrosine-based switch motif (ITSM). Following T-cell stimulation, PD-1 recruits the tyrosine phosphatases SHP-1 and SHP-2 to the ITSM motif within its cytoplasmic tail, leading to the dephosphorylation of effector molecules such as CD3 ζ , PKC θ and ZAP70 which are involved in the CD3 T-cell signaling cascade. The mechanism by which PD-1 down modulates T-cell responses is similar to, but distinct from that of CTLA-4 as both molecules regulate an overlapping set of signaling proteins. PD-1 was shown to be expressed on activated lymphocytes including peripheral CD4+ and CD8+ T-cells, B-cells, T regs and Natural Killer cells. Expression has also been shown during thymic development on CD4-CD8- (double negative) T-cells as well as subsets of macrophages and dendritic cells. The ligands for PD-1 (PD-L1 and PD-L2) are constitutively expressed or can be induced in a variety of cell types, including non-hematopoietic tissues as well as in various tumors. Both ligands are type I transmembrane receptors containing both IgV- and IgC-like domains in the extracellular region and contain short cytoplasmic regions with no known signaling motifs. Binding of either PD-1 ligand to PD-1 inhibits T-cell activation triggered through the T-cell receptor. PD-L1 is expressed at low levels on various non-hematopoietic tissues, most notably on vascular endothelium, whereas PD-L2 protein is only detectably expressed on

antigen-presenting cells found in lymphoid tissue or chronic inflammatory environments. PD-L2 is thought to control immune T-cell activation in lymphoid organs, whereas PD-L1 serves to dampen unwarranted T-cell function in peripheral tissues. Although healthy organs express little (if any) PD-L1, a variety of cancers were demonstrated to express abundant levels of this T-cell inhibitor. PD-1 has been suggested to regulate tumor-specific T-cell expansion in subjects with melanoma (MEL). This suggests that the PD-1/PD-L1 pathway plays a critical role in tumor immune evasion and should be considered as an attractive target for therapeutic intervention.

Pembrolizumab is a potent and highly selective humanized monoclonal antibody (mAb) of the IgG4/kappa isotype designed to directly block the interaction between PD-1 and its ligands, PD-L1 and PD-L2. Keytruda™ (pembrolizumab) has recently been approved in the United States for the treatment of patients with unresectable or metastatic melanoma and disease progression following ipilimumab and, if BRAF V600 mutation positive, a BRAF inhibitor.

4.1.2 Preclinical and Clinical Trial Data

Refer to the Investigator's Brochure for Preclinical and Clinical data.

There are currently no published reports regarding the use of checkpoint inhibitors in sarcoma. Two presentations were made at the 2016 ASCO meeting. In one study of twelve patients with uterine leiomyosarcoma no responses were seen. Another study looking at 40 patients with several histologies saw 5 responses (4 pleomorphic undifferentiated sarcomas and 1 synovial sarcoma). These results demonstrate that checkpoint inhibition may have activity for some patients with soft tissue sarcoma but that combination therapies will really be necessary to make it broadly applicable.

4.2.2 Rationale for Dose Selection/Regimen/Modification

The safety of Pembrolizumab has been evaluated extensively as a single agent. An open-label Phase I trial (Protocol 001) was being conducted to evaluate the safety and clinical activity of single agent Pembrolizumab. The dose escalation portion of this trial evaluated three dose levels, 1 mg/kg, 3 mg/kg, and 10 mg/kg, administered every 2 weeks (Q2W) in subjects with advanced solid tumors. All three dose levels were well tolerated and no dose-limiting toxicities were observed. This first in human study of Pembrolizumab showed evidence of target engagement and objective evidence of tumor size reduction at all dose levels (1 mg/kg, 3 mg/kg and 10 mg/kg Q2W). No MTD has been identified to date. Recent data from other clinical studies within the Pembrolizumab program has shown that a lower dose of Pembrolizumab and a less frequent schedule may be sufficient for target engagement and clinical activity.

PK data analysis of Pembrolizumab administered Q2W and Q3W showed slow systemic clearance, limited volume of distribution, and a long half-life (refer to IB). Pharmacodynamic data (IL-2 release assay) suggested that peripheral target engagement is durable (>21 days). This early PK and pharmacodynamic data provides scientific rationale for testing a Q2W and Q3W dosing schedule.

A population pharmacokinetic analysis has been performed using serum concentration time data from 476 patients. Within the resulting population PK model, clearance and volume parameters of Pembrolizumab were found to be dependent on body weight. The relationship between clearance and body weight, with an allometric exponent of 0.59, is within the range observed for other antibodies and would support both body weight normalized dosing or a fixed dose across all body weights. Pembrolizumab has been found to have a wide therapeutic range based on the melanoma indication. The differences in exposure for a 200 mg fixed dose regimen relative to a 2 mg/kg Q3W body weight based regimen are anticipated to remain well within the established exposure margins of 0.5 – 5.0 for Pembrolizumab in the melanoma indication. The exposure margins are based on the notion of similar efficacy and safety in melanoma at 10 mg/kg Q3W vs. the proposed dose regimen of 2 mg/kg Q3W (i.e. 5-fold higher dose and exposure). The population PK evaluation revealed

that there was no significant impact of tumor burden on exposure. In addition, exposure was similar between the NSCLC and melanoma indications. Therefore, there are no anticipated changes in exposure between different indication settings.

The rationale for further exploration of 2 mg/kg and comparable doses of pembrolizumab in solid tumors is based on: 1) similar efficacy and safety of pembrolizumab when dosed at either 2 mg/kg or 10 mg/kg Q3W in melanoma patients, 2) the flat exposure-response relationships of pembrolizumab for both efficacy and safety in the dose ranges of 2 mg/kg Q3W to 10 mg/kg Q3W, 3) the lack of effect of tumor burden or indication on distribution behavior of pembrolizumab (as assessed by the population PK model) and 4) the assumption that the dynamics of pembrolizumab target engagement will not vary meaningfully with tumor type.

The choice of the 200 mg Q3W as an appropriate dose for the switch to fixed dosing is based on simulations performed using the population PK model of pembrolizumab showing that the fixed dose of 200 mg every 3 weeks will provide exposures that 1) are optimally consistent with those obtained with the 2 mg/kg dose every 3 weeks, 2) will maintain individual patient exposures in the exposure range established in melanoma as associated with maximal efficacy response and 3) will maintain individual patients exposure in the exposure range established in melanoma that are well tolerated and safe.

A fixed dose regimen will simplify the dosing regimen to be more convenient for physicians and to reduce potential for dosing errors. A fixed dosing scheme will also reduce complexity in the logistical chain at treatment facilities and reduce wastage.

Although chemotherapy causes a temporary disruption in the immune response by inducing neutropenia and lymphopenia, chemotherapy also has the potential to bolster immunotherapy and create therapeutic synergy by directly removing barriers to the immune response such as regulatory T cells and myeloid derived suppressor cells (Ko, Kim et al. 2007, Hirschhorn-Cymerman, Rizzuto et al. 2009). Furthermore, the anti-tumor cytotoxic effects of chemotherapy can lead to increased presentation of tumor antigens by dendritic cells resulting in a tumor specific T cell response (Hirschhorn-Cymerman, Rizzuto et al. 2009, Tesniere, Schlemmer et al. 2010). In this proposal, we will test whether the addition of immunotherapy can bolster the efficacy of front line Doxorubicin in patients with STS by using the PD-1 inhibitor Pembrolizumab.

